3.2 Secondary Objectives

The secondary objectives of this study are:

- a) To compare the rates of cardiovascular and non-cardiovascular ED visits and re-hospitalizations rates, from discharge after index hospitalization for MI to 90 (+/-7) days follow-up between patients undergoing standard care alone or standard care plus the 12 lead ECG Smartheart home telemonitoring device.
- b) To compare the rates of downstream cardiovascular testing (echocardiogram, stress test or coronary CT, or invasive coronary angiogram) from discharge after index hospitalization for MI to 90 (+/-7) days follow-up between patients undergoing standard care alone or standard care plus the 12 lead ECG Smartheart home telemonitoring device.
- c) To compare the rates of MACE from discharge after index hospitalization for MI 90 (+/-7) days follow-up between patients undergoing standard care alone or standard care plus the 12 lead ECG Smartheart home telemonitoring device.
- d) To compare health care cost utilization (including all cardiovascular inpatient and outpatient office visits and tests) from discharge after index hospitalization for MI to 90 (+/-7) days follow-up between patients undergoing standard care alone or standard care plus the 12 lead ECG telemonitoring device.
- e) To compare quality of life (MacNew Heart Disease Questionnaire) from discharge after index hospitalization for MI to 90 (+/-7) days follow-up between patients undergoing standard care alone or standard care plus the 12 lead ECG telemonitoring device.

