4.2 Study Rationale

This study will be pursued as a prospective clinical trial building upon and extending the available evidence of the use of outpatient ECG monitoring after MI outlined above. We will test the clinical and economic impact of the SHL-telemonitoring cardiac device during the first 90 days after MI in a defined health care environment. The current standard of care is antiplatelet agents, beta blockers and statins alone, with a reported re-hospitalization rate of 17-25%. In addition to the standard care, patients in the intervention arm will be instructed on how to use the device and send ECG to a Mayo Clinic CICU designated study NP/PA, which will be in communication with the participant to respond to recordings taken for symptom review. Patients with a *true* acute cardiac event will be advised to seek medical assistance immediately, in case of STEMI, VT/VF or CAVB the EMS will be sent to the participant. Patients with reassuring ECG and low suspicion of acute cardiac event will be advised to postpone medical assistance and to avoid unnecessary emergency department [ED] visits. Such an approach may improve patient outcomes and reduce costs at the same time. Additionally, the COVID-19 pandemic brought its challenges to the health systems worldwide, those are uncertain times and prevention of unnecessary ED visits and readmissions after discharge would be beneficial, in particularly for patients post AMI having comorbidities.

[figure not shown]
It is important to emphasize that the device is safe to use and this is a very low risk study with a large potential benefit of decrease in unnecessary readmission rates, subsequent costs and early detection of real cardiac abnormalities with prompt medical assistance could improve outcomes. This study is planned to address the importance of home telemonitoring in cardiac patients and could have future implications on the current guidelines and standard care.

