In case of delay with conducting the phone call to the participant, >15 minutes from sending the ECG, or having any technical issues with recording the ECG, the participant will call to a study phone (number provided to the participant) carried by CICU NP/PA which is available 24/7. An alternative phone number will also be provided that will get the patient in touch with the Mayo Clinic operator who can then direct the patient to the Cardiac Intensive Care Unit (CICU) NP/PA staff. Patients will be instructed to use this if they are unable to reach the NP/PA staff directly with the previously provided phone number. In case the technical issue was not solved by the NP/PA, the recommendation for the patient will be based on the symptoms characteristics (as described in the NP/PA decision making tool). In case the participant cannot be reached by the primary phone number provided, NP/PA will call second provided phone number (of patients' related individual/significant other), in case there is no response to both phone numbers, and the participant did not call our NP/PA designated phone, further decisions will be based on the ECG tracing. If alarming findings are present, which may explain a loss of consciousness, EMS will be activated to the home address of the patient, assuming that patients will use the ECG device at home. If no alarming finding is present the patient will be reassured with a phone follow-up the next day.

Adverse Event Reporting

We will only be collecting adverse events that result in Cardiovascular Events, Emergency Department visits, and Hospitalizations, which will be looking at the outcomes, as this is a monitoring study, with no adverse events expected from the device (SmartHeart, which is FDA approved), as all other events are not relevant to the research study. To make sure assessments are consistent throughout the study, this will also be followed retrospectively.

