8.1 Schedule of Evaluations

Assessment	Screening, Enrollment, Randomization: pre-discharge (Day 0)	Week 1 (-3,+6 days)	Week 2 (-3,+6 days)	Week 4 (-3, +6 days)	Day 90 (Final) (+/- 7 days)
Informed Consent Form	X (R)				
Demographics	X				
Medical History	X				
Vital signs	X				
Physical Examination	X				
Current Medications	X				
Blood Chemistries	X				
Electrocardiogram	X				
Echocardiogram	X*				
Inclusion/Exclusion Criteria	X (R)				
Enrollment/ Randomization	X (R)				
Providing Device + Instructions	X (R)				
Quality of Life questionnaire (day 0)	X (R)				
Follow-up ECG and training call		X (R.S.)	X (R.S.)	X (R.S.Q)	
End of participation phone call, will include:					X (R)
• ED visits/Hospitalizations/MACE data /ccs					X (R)
• Current medications and if changed lately					X (R)
• Quality of Life questionnaire (day 90)					X (R)
Device collection (patient sending by mail)					X (R)

X Performed as standard of care (not specific for research)

X* If performed after the AMI event and pre-discharge

X (R) Research related only

X (R.S.) Research – Study group related only

X (R.S.Q) Research – Study group related only, depends on the need of further training beyond the first two tests.

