9.2. Sample Size and Randomization

Patients will be randomized to either standard medical therapy or the medical therapy plus the Smartheart 12 lead ECG home device.

The primary combined endpoint parameter is the rate of ED visits/rehospitalizations as well as related downstream cardiovascular testing (echocardiogram, stress test or coronary CT, or invasive coronary angiogram) at 90 (+/-7) days after discharge and mortality rates during the 90 (+/-7) days of follow up. Based on the most recent in-house registry data, we have about 50 AMI patients undergoing PCI a month. Accordingly, we have at least 600 patients a year who are discharged with a diagnosis of AMI from Saint Mary's Hospital.

Our own registry data further indicate that 24% of revascularized AMI patients will present to the ED or will be readmitted within 90 days. This is in keeping with the published literature citing a rate of 20-30%. Half of these patients will present for cardiovascular complaints and may get further testing, including echocardiogram, stress test or coronary CT, or invasive coronary angiogram. Having a 12-lead ECG available and the phone triage available to direct care may impact not only emergency presentation but also downstream testing. This will be considered in this trial, and each of these will be considered as a component to the combined primary endpoint event. Assuming that patients presenting with cardiovascular concern may receive two of the outlined downstream test as they present to the ED and hospital, the estimated event rate will be 48%. With 120 patients in each arm the study we would be adequately powered (beta error <0.2) to show a statistically significant (at alpha error levels of <0.05) for a 37.5% event reduction.

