9.5.1.1. Primary outcome measures

The combined primary endpoint of the trial is the rate of ED visits, hospital readmission, and any of the downstream testing modalities (echocardiogram, stress test or coronary CT, or invasive coronary angiogram) from discharge after index hospitalization for MI to 90 days of follow-up between group 1 and group 2.

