9.5.2.1. Outcome measures

- Rate of ED visit and rehospitalization, overall and related to cardiovascular and non-cardiovascular causes
- Rate of downstream testing modalities (echocardiogram, stress test or coronary CT, or invasive coronary angiogram)
- Rate of MACE as defined above
- Amount of money in US dollars that was spent for any medical service related to cardiovascular and non-cardiovascular diseases in both study groups.
- Quality of life questionnaire score in both study groups at the time of enrollment and at 90 days.

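### The visit outcomes and the day-90 call omit unscheduled clinic and urgent-care visits, so a shift of care away from the ED could pass as fewer visits, and its cost could be missed if it occurs off site

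*Combined protocol and SAP*

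**What the plan says.** **Visits.** The primary endpoint (9.5.1.1) is "the rate of ED visits, hospital readmission, and any of the downstream testing modalities". The listed tests are echocardiogram, stress test or coronary CT, and invasive angiogram. The secondary visit outcome (9.5.2.1) is "Rate of ED visit and rehospitalization, overall and related to cardiovascular and non-cardiovascular causes". Neither includes an unscheduled clinic or urgent-care visit.

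**Collection.** The day-90 telephone call is the only outcome contact that 8.1 schedules in both arms; the calls at weeks 1, 2 and 4 are for the device arm only. Its health-care item reads "ED visits/Hospitalizations/MACE data /ccs"; medications and quality of life are also covered. Adverse-event collection (section 5) is similarly limited: "We will only be collecting adverse events that result in Cardiovascular Events, Emergency Department visits, and Hospitalizations".

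**Cost.** Secondary objective 3.2(d) defines cost as "including all cardiovascular inpatient and outpatient office visits and tests". Section 9.5.2.1 is wider: "Amount of money in US dollars that was spent for any medical service related to cardiovascular and non-cardiovascular diseases in both study groups". Both scopes take in outpatient care. Neither names a data source.

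**Intervention.** Under 4.2, device patients with a reassuring ECG and low suspicion of an acute event "will be advised to postpone medical assistance and to avoid unnecessary emergency department [ED] visits". Control patients receive no such call.

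**The concern.** The intervention acts directly on where patients seek care, and it does so in one arm. Suppose a device patient is advised against the ED, attends an urgent-care centre or an unscheduled clinic appointment instead, and has no listed test. That patient counts as event-free. A control patient who takes the same complaint to the ED counts as an event. The visit outcomes cannot distinguish the first patient from one who needed no care at all.

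This matters because the study summary hypothesises fewer ED presentations and readmissions together with lower health-care cost. An avoided visit and a relocated visit mean different things for that joint claim. The cost outcome is where the difference should appear, and it depends on outpatient data that the patient contact is not set up to gather.

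**Working it through.** **1. Definition against collection**

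| Type of care | Primary (9.5.1.1) | Secondary visit rate (9.5.2.1) | Cost (3.2 d, 9.5.2.1) | Day-90 call (8.1) |
|---|---|---|---|---|
| ED visit | yes | yes | yes | yes |
| Readmission | yes | yes | yes | yes |
| Listed test, wherever ordered | yes | no (separate test rate) | yes | not listed |
| Unscheduled clinic or urgent-care visit, no listed test | no | no | yes | not listed |

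The last row is the gap. The cost definition requires the item, no visit outcome counts it, and the call does not ask for it. Section 10.2 describes extraction from medical records in general terms but does not say how care given elsewhere is found.

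**2. The plan's own power figure**

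Inputs from 9.2 and 9.6: 120 per arm, control rate 48%, reduction 37.5%, alpha 0.05 (taken as two-sided, since the plan does not say), chi-square test.

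- Device rate: 0.48 × (1 − 0.375) = 0.30. Pooled rate: 0.39.
- SE under the null: √(2 × 0.39 × 0.61 / 120) = 0.0630.
- SE under the alternative: √((0.48 × 0.52 + 0.30 × 0.70) / 120) = 0.0619.
- Power: Φ((0.18 − 1.96 × 0.0630) / 0.0619) = Φ(0.91) = 0.82.

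This agrees with the stated beta below 0.2.

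**3. Illustration of relocation**

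Assume that total care does not change and that a share f of device-arm events moves to uncounted visits. The device rate becomes p × (1 − f). The documents give no value for f; 10% and 20% are assumptions. Two bases are shown: the 48% composite rate and the 24% rate for ED visits or readmissions alone. For the latter, 9.2 says that "24% of revascularized AMI patients will present to the ED or will be readmitted within 90 days". The last column is the exact rejection probability of the uncorrected two-sided 5% chi-square with 120 per arm.

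| Base p | f | Device rate | Normal approximation | Exact |
|---|---|---|---|---|
| 48% | 10% | 43.2% | 0.112 | 0.110 |
| 48% | 20% | 38.4% | 0.322 | 0.321 |
| 24% | 10% | 21.6% | 0.065 | 0.073 |
| 24% | 20% | 19.2% | 0.145 | 0.149 |

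If half of the relocated patients still had a listed test, only f/2 would leave the endpoint. The exact figures would then be 0.061 (f = 10%) and 0.110 (f = 20%) on the 48% base, and 0.056 and 0.073 on the 24% base. The nominal level is 0.05.

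**4. Visits at risk of being left out of cost**

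On the 24% base, 10–20% relocated is 0.10 × 24 = 2.4 to 0.20 × 24 = 4.8 visits per 100 device patients, at one visit per patient. If 20–50% of these were off site (assumed), 0.20 × 2.4 = 0.5 to 0.50 × 4.8 = 2.4 per 100 could be missing from the cost total. The documents give no unit costs, so no dollar figure follows.

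**The case against.** Several points on the other side are sound.

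- **Relocation is an inference.** The readable text advises low-suspicion patients to postpone care; it does not send them to a clinic or to urgent care. The call work-flow (Figure 2) is not shown and the NP/PA decision tool is not in the text supplied. A reader might infer that triage moves care to those settings, but the documents neither confirm nor exclude it.
- **Cost covers this care by definition.** A reader might infer that relocated care would simply be reported as lower cost. Sections 3.2(d) and 9.5.2.1 do not support that. The weakness is in collection only, and only for visits that the site's records do not show. The investigator-designed case report forms are not supplied and may ask for more.
- **Fewer ED visits is the stated aim.** If a patient is managed in clinic instead of the ED, the ED reduction is real and Aim 1 is reported correctly.
- **Relocated care is not wholly invisible.** Section 9.5.1.1 counts a listed test wherever it is ordered, and MACE and quality of life are compared as well.
- **Control patients may also use a clinic instead of the ED.** What is confined to one arm is the advice.
- **A larger size is tempting.** If the whole planned 37.5% reduction were relocation, the test would reject with probability 0.83 on the 48% base (0.43 on the 24% base). But 0.83 is the trial's design power under another name. It also requires counted tests to disappear along with the visits, which would be a real fall in care. On the 24% base, it requires readmissions to become clinic visits.

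None of this fills the gap in the last row of the table. The cost outcome needs an item that the call does not list, and without that item the trial cannot show whether ED visits were avoided or moved.

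**Conclusion.** The concern holds in a limited form. Unscheduled clinic and urgent-care visits are absent from the visit outcomes and from the day-90 call. The cost outcome includes them, but no collection route from patients is visible. Since the advice to postpone care is given in one arm only, any shift to other settings without a listed test would appear as fewer visits, and its cost could be under-captured if it occurs off site.

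The calculated probabilities are an illustration, not an estimate of bias. They assume 10–20% relocation, no true change in total care, and no listed test among relocated patients. Under those conditions the chance of a significant result is about 11–32% on the 48% base and 7–15% on the 24% base, and it falls if some relocated patients are tested.

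The documents do not support the claim that the trial would report a false success on visits or cost. They support a narrower one: as written, the visit data could not separate avoided from relocated care.

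**What to change.** 1. **Section 8.1.** Add to the day-90 call, in both arms and with identical wording, the number and place of unscheduled clinic and urgent-care visits since discharge.
2. **Sections 3.2(d) and 9.5.2.1, cost.** Use these answers in the cost total and name the other data sources. Reconcile the cardiovascular-only scope of 3.2(d) with the cardiovascular and non-cardiovascular scope of 9.5.2.1.
3. **Section 9.5.2.1, outcomes.** Add any unscheduled acute contact (ED, urgent care or unscheduled office visit) as a supportive secondary outcome, analysed like the primary and reported beside it.
4. **Section 9.5.1.1.** Leave the primary endpoint unchanged.

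The cost is one question in an existing call and one more secondary analysis. Neither the sample size nor the triage process changes. The downside is recall error over 90 days, to which the call's existing ED and hospitalization items are also exposed. If the case report forms or the cost data source already capture these visits, it is enough to say so in 8.1 and 9.5.2.1 and to add the supportive outcome.

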9.5.2. Secondary trial objective

The second aim of the trial is to compare the individual endpoints of the primary endpoint, MACE rates, health care utilization costs and quality of life between group 1 and group 2.

9.5.2.1. Outcome measures

- Rate of ED visit and rehospitalization, overall and related to cardiovascular and non-cardiovascular causes
- Rate of downstream testing modalities (echocardiogram, stress test or coronary CT, or invasive coronary angiogram)
- Rate of MACE as defined above
- Amount of money in US dollars that was spent for any medical service related to cardiovascular and non-cardiovascular diseases in both study groups.
- Quality of life questionnaire score in both study groups at the time of enrollment and at 90 days.

9.6. Data Analyses

The primary analysis for Aim 1 (lead aim of the study) will be a comparison of the rates of the primary combined endpoint between group 1 and 2 via Chi square test for categorical data of independent samples. The test will be used for any other categorical data. For continuous data, an independent groups t-test or Wilcoxon as appropriate after testing distributional assumptions.

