Number of Subjects	240 patients in total, enrolled over one-two years

Inclusion and Exclusion Criteria	
Inclusion criteria:
 
 • ≥18 years of age, • Acute myocardial infarction, both STEMI and non-STEMI • Able to use the home ECG telemonitoring • Must have smartphone device with home wi-fi/mobile internet which allows 24/7 ability to transmit ECG • Caring family member who will be able to help/perform the ECG in case the patient himself won't be able to do it • Planned to be discharged home by the treating team 
Exclusion criteria:
 
 • No ability to use the device at home • No smartphone device or home wi-fi/mobile internet which prevent 24/7 ability to transmit ECG • Cannot download the smartheart app • No support in home environment • Out of hospital cardiac arrest: secondary to a non-shockable rhythm, unrelated to an acute coronary syndrome, or with any level of neurologic damage. • Resident of nursing home or acute care facility • Uninterpretable ECG at discharge – left bundle branch block (LBBB), pacemaker or implantable cardioverter defibrillator (ICD) with pacing dependence. • Patients who are planned for staged PCI after the index hospitalization
Study Product, Dose, Route, Regimen	Prior to discharge patients will be 1:1 randomized to standard medical therapy or standard medical therapy + 12 lead ECG Smartheart telemonitoring device.
Duration of Administration	Patients will receive the device for the period of 90 (+/-7) days .
Reference therapy	Group 1 will serve as the reference group
Statistical Methodology	Inter-group differences in the rates of the primary combined endpoint will be analyzed by the Chi square test.

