4. BACKGROUND AND RATIONALE

4.1 Background

Survivors of a first acute myocardial infarction (AMI) face a substantial risk of further major adverse cardiovascular events (MACE), including death, recurrent MI, heart failure, arrhythmias, angina, and stroke. The rate of rehospitalization within 30 days after acute MI is reported to range between 17 and 25 percent [1,2]. In a single-community study, Olmsted County, Minnesota, United States, of 3010 patients who were hospitalized for a first-ever MI (STEMI – 31%) rehospitalization within 30 days occurred in about 19 percent [3]. Across the broad spectrum of patients with acute myocardial infarction (MI), short-term (in-hospital or 30-day) mortality has been decreasing over the past 30 years, concomitantly with the increasing use of reperfusion strategies and proven preventative therapies such as beta blockers, aspirin, and statins [4-12]. The 30-day mortality after all acute coronary syndromes (ST-elevation myocardial infarction [STEMI], non-ST elevation myocardial infarction [NSTEMI], and unstable angina) is less than 5 percent [13]. The incidence of SCD after acute MI is the same with STEMI and NSTEMI [4,14]. Among patients who have had an MI and are followed for about four years, approximately one-half of sudden deaths occur in the first year and one-quarter in the first three months [15,16]. The risk is markedly increased in patients with a left ventricular ejection fraction ≤ 35 percent. Additional important aspect following acute MI [AMI] is financial, although mortality attributable to AMI has declined, 30-day post-AMI readmission rates remain high (median 19.9%) and carry a heavy economic burden, accounting for 21,000 admissions at a cost of 136 million dollars in the United States [17].

“SHL”-Telemedicine is a call center that was established in 1987 in Israel. It operates 24 hours/day, 365 days a year, and is managed by a medical staff. Each subscriber’s medical file (which also includes a full 12-lead

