8.1.2 Enrollment, Baseline, and/or Randomization

All patients who consent to the study are considered to be enrolled as of the date of the consent.

Baseline Assessments- comprises a review for any cardiovascular diseases or risk factors, home medications. Additional data will be collected: type of AMI (location: anterior, inferior, posterior, lateral), troponin levels, baseline ECG, left ventricular function by echocardiography, Canadian Classification scale (CCS) of Angina(class I, II, III IV) .

Randomization- will be done once all inclusion and exclusion criteria are reviewed and the patient meets eligibility criteria. Patient and treating cardiologist will be informed which study group the patient was assigned. Patients assigned to group 1 will be discharged with standard medical therapy as indicated by AHA/ACC guidelines in post AMI patients treated with or without PCI. Patients in group 2 will be discharged with the standard medical treatment as indicated by AHA/ACC guidelines in post AMI patients treated with or without PCI plus they will receive the Smartheart 12 lead ECG home telemonitoring device for the period of 90 days (+/-7). Those patients will have short explanation on how the device works, how to adjust it on the chest and how to transmit the ECG.

A post-study questionnaire will be administered to patients randomized to the device group to collect feedback on their experiences with the device. Participation is voluntary, and responses will be anonymized to ensure confidentiality. The inclusion of this questionnaire will not impact the primary study objectives or patient safety.

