10.2. Data Management

All study data will be collected at Mayo Clinic with the Department of Cardiovascular Diseases as the primary coordinating and data management center.

RedCap will be used for clinical data management and randomization. These tools are institutionally supported and allow for rapid database development. The implementation of the software within a project includes training on the system's use, robust error checking, security considerations, and full audit trail. Balance, which is integrated into *RedCap*, allows for a variety of randomization and minimization algorithms.

Demographic and clinical data will be extracted from medical records including age and gender, vital signs, physical exam findings.

Data on clinical outcome/event reporting will include cardiac dysfunction and/or heart failure as well as major adverse cardiovascular events (including myocardial infarction, heart failure, arrhythmia, transient ischemic attack, and stroke).

The echocardiographic parameters that will be captured comprise systolic, diastolic LV and RV function including LVEF.

The angiographic parameters collected will include name of the coronary artery, degree of stenosis and location, number of diseased vessels and number of stents, PCI success and complications.

All individually identifiable patient records and data will be stored in a database under coded accession numbers. A password is required to gain access to this protected and privileged information. Only the approved and trained study staff will have access to the database. The sponsor will not have any access to the study data. For individuals providing data, e.g. core laboratory personnel, access will be limited to entering data only. All data are monitored regularly for entry and access, and a formal policy regarding protection of personal privacy is in place throughout Mayo Foundation. The key to identification of subjects will be maintained in a secure office environment under the direction of the investigators. The institutional commitment at Mayo Clinic to protect patients' (and study participants') privacy is a high priority.

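### The primary analysis is a valid but unadjusted chi-square that leaves baseline data recorded in both arms unused, forgoing a modest gain in precision

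*Combined protocol and SAP*

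**What the plan says.** Section 9.6 defines the primary analysis as a "comparison of the rates of the primary combined endpoint between group 1 and 2 via Chi square test for categorical data of independent samples" and applies the same test to other categorical data. The Statistical Methodology row of the Study Summary agrees: "Inter-group differences in the rates of the primary combined endpoint will be analyzed by the Chi square test". Neither place mentions a covariate, a stratified test or a regression model.

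Section 8.1.2 sets out a baseline assessment ahead of randomization. It covers cardiovascular disease, risk factors, home medications and CCS class, and also "type of AMI (location: anterior, inferior, posterior, lateral), troponin levels, baseline ECG, left ventricular function by echocardiography". Section 10.2 adds age from the medical record. Section 6.1 admits both STEMI and NSTEMI.

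Section 9.3 describes a computer-generated 1:1 scheme and names no stratification factor. Section 10.2 says only that the randomization tool "allows for a variety of randomization and minimization algorithms".

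On power, section 9.2 describes 120 per arm as "adequately powered (beta error <0.2") "at alpha error levels of <0.05) for a 37.5% event reduction", starting from a 48% event rate.

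**The concern.** A randomized comparison of a yes/no outcome can use prespecified baseline predictors without changing its question. A logistic model, averaged over the trial population, still estimates the difference in 90-day risk between arms. It does so with less variance if the covariates predict the outcome. The plan records candidate predictors in both arms and uses none of them.

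Two features make this worth raising. First, the power margin is thin: 115 per arm is the minimum for 80%, the plan has 120, and no dropout allowance is stated. Second, the trial mixes infarct types without stratifying. As an illustration, take the 31% STEMI share of the community cohort cited in section 4.1. The between-arm difference in STEMI share then has standard deviation √(2 × 0.31 × 0.69 / 120) = 0.060, so chance differences of up to about 12 percentage points lie within the 95% range. If infarct type predicts the endpoint, such a difference carries into the unadjusted estimate. Covariates chosen after the data are seen would not be credible, so the list must be fixed beforehand.

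**Working it through.** **Inputs.** Control rate 48%, relative reduction 37.5% and 120 per arm come from section 9.2, and 1:1 allocation from section 9.3. Alpha is 0.05; sidedness is not stated and is taken as two-sided. The intervention rate is 0.48 × (1 − 0.375) = 0.30. The share of outcome variance explained by baseline covariates, R², is not in the documents. It is an assumption, shown over 0 to 0.10.

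**The plan's own figure.** The pooled rate is 0.39.

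- SE under the null: √(2 × 0.39 × 0.61 / 120) = 0.0630
- SE under the alternative: √((0.48 × 0.52 + 0.30 × 0.70) / 120) = 0.0619
- Power: Φ((0.18 − 1.96 × 0.0630) / 0.0619) = Φ(0.914) = 0.820

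The stated power above 80% is reproduced.

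**With adjustment.** The effective sample size per arm is 120 / (1 − R²), entered in the same formula. The number needed for 80% power is 115 × (1 − R²), rounded up. The last column uses the 24% per-patient rate of ED presentation or readmission in section 9.2 with the same relative reduction: 0.24 × 0.625 = 0.15.

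| Assumed R² | Effective n per arm | Power, 48% vs 30% | n per arm for 80% power, 48% vs 30% | Power, 24% vs 15% |
|---|---|---|---|---|
| 0 | 120.0 | 0.820 | 115 | 0.420 |
| 0.02 | 122.4 | 0.827 | 113 | 0.427 |
| 0.05 | 126.3 | 0.839 | 110 | 0.438 |
| 0.10 | 133.3 | 0.858 | 104 | 0.458 |

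R² of 0.02 to 0.10 is thus worth about 2 to 13 extra patients per arm.

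**Check by simulation.** Each row has 5,000 trials of 120 per arm at 48% vs 30%, with one standard-normal prognostic covariate. The adjusted analysis is a logistic model standardized to the risk difference, with an influence-function standard error corrected for degrees of freedom. The variance ratio is adjusted over unadjusted. The Monte Carlo standard error of each power is about 0.005.

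| R² | Added noise covariates | Chi-square power | Adjusted power | Variance ratio |
|---|---|---|---|---|
| 0.05 | 0 | 0.822 | 0.837 | 0.948 |
| 0.09 | 0 | 0.837 | 0.863 | 0.912 |
| 0.09 | 4 | 0.821 | 0.853 | 0.933 |
| 0.03 | 4 | 0.823 | 0.835 | 0.998 |
| 0 | 4 | 0.825 | 0.818 | 1.021 |

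Without noise covariates, the adjusted type I error was 0.050 to 0.053. The last row gives the cost when nothing is prognostic: 0.825 − 0.818 = 0.007, under 1 point. In the row above it, weak prognosis with four useless covariates gives almost no gain in precision. Part of the apparent power difference there is test size: null rejection was 0.054 adjusted against 0.047 for the chi-square.

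**Length of the covariate list.** In further simulations with assumed category frequencies and effects, a model of about eight covariate parameters (age, STEMI/NSTEMI, three-level LVEF, four-level CCS, prior disease) gave variance ratios of 1.00 to 1.03 under weak or no prognosis. Its type I error was 0.058 to 0.062 without a small-sample correction. A three-covariate model gave ratios of about 0.93 to 0.99 under weak to moderate prognosis. Its corrected type I error was 0.055 to 0.058, against 0.054 to 0.057 for the chi-square.

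**The case against.** The strongest defence is that nothing here is wrong. Under randomization the chi-square's error rate already allows for chance imbalance, the test matches the sample-size method, and section 5 calls the study a pilot. All of that stands. Imbalance is a reason to seek precision; it does not make the test invalid.

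The second defence is that the benefit is assumed. This also stands. The only prognostic statement in the documents, that risk is "markedly increased in patients with a left ventricular ejection fraction" of 35% or less (section 4.1), concerns sudden death. The composite is ED visits, readmission and testing, and section 9.2 expects only half of those who present to have cardiovascular complaints. R² may lie at the low end.

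A reader might infer three stronger points that the documents do not support:

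- **A variance reduction near 16%.** This needs far stronger prediction (R² of about 0.17 in these simulations), and nothing in the plan points to it.
- **A misstated standard error from minimization.** Section 10.2 describes what the software can do. Section 9.3 plans no minimization and names no factors.
- **Waste of data the trial pays for.** The schedule in section 8.1 marks history, examination, blood tests, ECG and echocardiogram as standard of care.

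There are also limits on which covariates can serve. Echocardiography is captured only if performed, so LVEF may be missing. CCS is listed at baseline in section 8.1.2, but the schedule shows it only at day 90. Section 8.1.2 defines infarct type by location, so STEMI/NSTEMI has to be taken from the eligibility record.

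**Conclusion.** The point holds as a modest improvement. At 48% against 30%, prespecified adjustment would raise power from 0.82 to about 0.83 to 0.86 if baseline covariates explain 2% to 10% of outcome variance. It would cost under 1 point if they explain none. That range is an assumption; the documents give no figure. The gain also depends on a short covariate list and a corrected standard error.

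It would be wrong to infer that adjustment rescues the sample size. The 48% appears to be 24% + 2 × 12%, which adds tests to patients, whereas a chi-square needs one yes/no per patient. If the per-patient rates are nearer 24% and 15%, power is 0.42 unadjusted and at most 0.46 over the same R² range. That is a separate and larger problem, which this change does not touch.

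**What to change.** In section 9.6 and the Statistical Methodology row of the synopsis, make the primary analysis a logistic regression of the combined endpoint on:

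- arm;
- age, STEMI/NSTEMI and prior cardiovascular disease, each recorded for every patient;
- any factor actually used in randomization, to be named in section 9.3.

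Report the standardized marginal risk difference with a robust, small-sample-corrected 95% CI. Keep the unadjusted chi-square as a supporting analysis. Leave LVEF and four-level CCS out of the primary model, or collapse them, with a stated rule for LVEF not measured. List STEMI/NSTEMI as a baseline variable in section 8.1.2. State in section 9.4 whether the sample-size re-estimation keeps the unadjusted formula.

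The cost is protocol wording and one model, with no extra patients and no new measurements. The downside is a slightly less simple primary analysis and under 1 point of power if the covariates turn out not to be prognostic.
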